The COVID-19 patient population has increased risk for vascular events and these events are monitored as part of standard of care. Standard of care will be followed, and diagnostics may include lab values and imaging studies. Additionally, PT, PTT, INR, platelets, and TEG labs will be drawn before and after the infusion and the study team will monitor the study participants by observing their clinical progress/course for any such clinically significant vascular events that occur during the study period. These events will report them as adverse events as part of good clinical research practice.

Reporting to the UMB HSR-IRB and DSMB:

The Principal Investigator or designee is responsible for reporting SAEs and unanticipated problems to the site IRB according to the participating site institutional guidelines. (Please see the revised additional information form details)

Reporting to the FDA:

The PI for the study is responsible for providing safety updates to the FDA per the guidelines. The reporting times refer to the time the study team received knowledge of the AE. Please see the attached Table 1 for details.

Sample Size and Statistical Analysis:

The study aims to maximize knowledge on the use of Regadenoson to treat COVID-19 in order to plan for a larger trial. Safety analysis will be prioritized to allow for the expansion to a multi-site trial. The study will enroll moderate and severely ill subjects to maximize enrollment at the single enrolling institution. Severity of illness and baseline respiratory failure will be delineated within the analysis to account for the variability in the patient population. This trial will provide estimates of outcome variability in the primary and secondary outcomes that will be valuable for planning a larger randomized trial. Additionally, in planning for a larger trial, exploratory analyses will adjust estimates of treatment differences by known risk factors. Although we recognize that these

analyses will be limited by the number of observed events, they will be useful for decisions on eligibility criteria or stratification factors in the larger trial. The analyses will be carried out on data from all randomized participants.

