We will enroll 40 moderate to severe COVID-19 patients, which is defined in the inclusion criteria above. Following the recommendation of the FDA review of our IND application, the trial focuses on providing estimates of outcome variability in the primary and secondary outcomes that will be valuable for planning a larger randomized trial. Additionally, in planning for a larger trial, exploratory analyses will adjust estimates of treatment differences by known risk factors. Due to the mixture of the moderate to severe COVID-19 patients with various baseline severity levels, we will record information regarding each patient, such as age, sex, race, symptoms, vital signs, saturation of oxygen, medications, treatments, days of illness, comorbidities, chest Xray imaging, and baseline severity (such as, whether on oxygen, on ventilator, or on ECMO etc.) prior to Regadenoson infusion. When we analyze the effects of Regadenoson on COVID-19 patients, we can do exploratory analyses within subgroups of these patients and conduct primary efficacy analysis and propose appropriate methods of covariate adjustment. The prevention and treatment of respiratory failure will be analyzed within appropriate subgroups. For each subject, we will clearly document the reason for hospital admission, document the standard of care followed for each subject, and if care decisions are made based on resource limitation.

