The primary outcome is the proportion of patients alive and free of respiratory failure through the 30-day trial. The total sample size of 40 participants will be randomized equally between the usual care and Regadenoson groups, using a randomly permuted block design, with random block sizes of 2 and 4. This plan will be generated by the study statistician. Within each group, the primary outcome proportion can be estimated with a standard error of no more than 11 percentage points; the difference between the groups can be estimated with a standard error that is no more than 16 percentage points. These calculations are based on the most conservative estimate in terms of standard error, using a proportion of 50% in each group. If, as expected, the proportions in each group are greater, such as 80% in usual care and 90% in the Regadenoson group, the difference can be estimated with a standard error of 11 percentage points. While these are relatively large standard errors, they are adequate to meet the objective suggested by the IND review, providing estimates of outcome proportions to be used in a larger trial.

To assess safety, the DSMB statistician will tabulate sequentially the proportion of participants in each group who unexpectedly experience serious cardiovascular side effects or persistent (> 30 min) intolerable side effects, based on clinical experience with Regadenoson. Intolerable side effects include headache or dyspnea. If the lower bound of a one-sided 80% confidence interval for the difference in proportions exceeds 10%, we will pause the trial, examine the adverse event profiles, and consider modifying dosing. With this rule, if the true proportion of patients who experience serious side effects is 20% in each group, there is a 16.5% chance that the trial will be paused; if the

true proportion with Regadenoson is 40%, there is a 58% chance the study will be paused.

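### Forty patients are randomized from one unstratified list and compared by an unadjusted difference, so chance imbalance in baseline respiratory failure costs precision that a single stratification factor would largely recover

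*Combined protocol and SAP*

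**What the plan says.** The allocation paragraph of Sample Size and Statistical Analysis assigns the 40 patients 1:1 to the two arms. The method is given as "using a randomly permuted block design, with random block sizes of 2 and 4". No stratification factor is named there or elsewhere. The same section mentions stratification factors only as a decision for the larger trial.

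Exclusion criterion 11 removes patients only after more than 72 hours of respiratory failure, so those with a shorter duration may enter. Ventilator and ECMO are listed among the baseline severity states. The Primary Endpoint is being alive and free of respiratory failure through the 30-day trial.

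On this factor the plan says: "Severity of illness and baseline respiratory failure will be delineated within the analysis to account for the variability in the patient population", and later: "The prevention and treatment of respiratory failure will be analyzed within appropriate subgroups". Adjustment for known risk factors is described as exploratory and limited by the number of events. The closing paragraph of the section plans a one-sided 90% confidence interval for the difference in Kaplan-Meier failure-free survival at 30 days, with no stratum or covariate.

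On precision the plan says "the primary outcome proportion can be estimated with a standard error of no more than 11 percentage points" and "the difference between the groups can be estimated with a standard error that is no more than 16 percentage points". For example rates, "such as 80% in usual care and 90% in the Regadenoson group", it says "the difference can be estimated with a standard error of 11 percentage points".

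**The concern.** Baseline respiratory failure is known before allocation, because criterion 11 cannot be checked without it. It overlaps the definition of the endpoint, so it is likely to be strongly prognostic. A single permuted-block list balances total numbers only. It controls neither how patients already in respiratory failure divide between arms nor the arm sizes within the prevention and treatment subgroups. Because the planned interval is for a crude difference, any chance imbalance passes straight into the estimate.

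What is at stake is the precision of the trial's main product: an estimate for planning a larger trial, from about 20 patients per arm.

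**Working it through.** **1. The plan's own figures.** With n = 20 per arm:
- One arm at 50%: √(0.25/20) = 11.2 points (plan: 11).
- Difference at 50%/50%: √(0.50/20) = 15.8 points (plan: 16).
- Difference at 80%/90%: √((0.16 + 0.09)/20) = 11.2 points (plan: 11).

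All three reproduce.

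**2. Inputs not in the documents.** Let K be the number of the 40 who enter in respiratory failure, and g the gap in success rate between patients without and with it. Both are assumptions. I also assume that all 40 are randomized.

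**3. Size of the chance imbalance.** With 20 per arm, the number a of such patients in one arm is hypergeometric(40, K, 20). The between-arm gap in prevalence is |2a − K|/20.

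| K | SD of gap (points) | P(arms differ by ≥4 patients) | P(≥6) |
|---|---|---|---|
| 4 | 9.6 | 0.11 | 0 |
| 6 | 11.4 | 0.18 | 0.02 |
| 8 | 12.8 | 0.24 | 0.04 |
| 12 | 14.7 | 0.30 | 0.08 |

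Simulation of the plan's own random blocks of 2 and 4 gives nearly the same SDs and, for K = 12, about 30% and 8%.

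**4. Effect on the crude difference.** Shift = (imbalance/20) × g. For a 4-patient imbalance the first term is 0.20.
- 60% against 15% failure (g = 0.45): 0.20 × 0.45 = 9 points. A 6-patient imbalance gives 0.30 × 0.45 = 13.5 points.
- All baseline-failure patients count as failures, others fail at 15% (g = 0.85): 0.20 × 0.85 = 17 points.
- g = 0.30: 0.20 × 0.30 = 6 points. A shift of 10 points or more then needs an imbalance of at least 0.10/0.30 × 20 = 6.7 patients; its probability is 0-3% for K from 4 to 20.

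**5. Consistency with the plan's 80% in usual care.** If every baseline-failure patient counts as a failure, K/40 cannot exceed 20%, so K is at most 8. The others' success rate would be 0.80/(1 − K/40): 0.89 at K = 4 and 1.0 at K = 8. A shift above 10 points, in either direction, then has probability 11% (K = 4) to 24% (K = 8). Under 60% against 15%, K = 4 gives 0.10 × 0.60 + 0.90 × 0.15 = 19.5% failure, which fits the 80%. K = 12 gives 0.30 × 0.60 + 0.70 × 0.15 = 28.5%, which is more pessimistic than the plan's example.

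**6. Precision, K = 12, 60% against 15%, no treatment effect.**
- Within-stratum variance: (0.3 × 0.24 + 0.7 × 0.1275) × (2/20) = 0.01613.
- Variance from imbalance: (0.147 × 0.45)² = 0.0044.
- Crude SE, one list: √(0.01613 + 0.0044) = 14.3 points (14.2 in simulation).
- Stratified lists: about √0.01613 = 12.7 points (12.7 in simulation).
- One list with a post-stratified estimate: 12.9 points in simulation.

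For K = 4 the same arithmetic gives a within-stratum part of (0.1 × 0.24 + 0.9 × 0.1275) × 0.1 = 0.01388 and an imbalance part of (0.096 × 0.45)² = 0.0019. The SE falls from 12.5 to 11.8 points.

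**7. What stratified lists guarantee.** Only the last block in a stratum can be incomplete, and with blocks of 2 and 4 it leaves at most 2 patients unmatched. Each stratum is therefore off by at most 2, and the total by at most 4.

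**The case against.** The strongest reply is that analysis alone can do most of the work: post-stratifying the single list gives 12.9 points against 12.7 with stratified lists. That stands. The gap lies at least as much in the crude primary interval as in the allocation. Where few patients enter in respiratory failure, though, the lists still matter. With K = 4, a difference of 4 means all four are in one arm, which happens in 11% of trials and leaves that stratum with no comparison.

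The plan can also say that it accepts large standard errors in an estimation study, leaves stratification to the larger trial and foresees covariate adjustment. This too stands: one list at a single centre is a defensible choice. The adjustment, however, is exploratory and has no stated method.

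The subgroup argument is modest. At 50% failure, a 9 against 3 split gives an SE of √(0.25/9 + 0.25/3) = 33 points, and 6 against 6 gives 29. Neither is informative.

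A reader might infer more than the documents support:
- That the estimate is biased or the stated standard errors are wrong. Randomization without strata is unbiased over repetitions, and chance imbalance is already inside those binomial standard errors.
- That imbalance will typically exceed the effect the trial hopes to find. The 80% and 90% are an illustration for a standard error, not a design target. In the 60% against 15% case, a 4-patient imbalance moves the result by 9 points, which is below 10.
- That the plan ranks this factor above others. It names it alongside severity of illness as something to delineate.
- That the all-fail case can be combined with 12 or more such patients. This conflicts with 80% success in usual care. The all-fail reading also arises from a separate ambiguity: how the endpoint treats patients who enter already in respiratory failure. Stratifying does not resolve that.

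**Conclusion.** The point holds as a modest, inexpensive gain in precision. The design is valid without it. For one realistic scenario (12 of 40, 60% against 15% failure) the true standard error would fall by roughly a tenth; with 4 of 40 the gain is smaller. Under a weak prognostic gap there is little to gain. If patients who enter in respiratory failure all count as failures, the crude difference is much more exposed to imbalance.

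The size depends on the prevalence of baseline respiratory failure and on its prognostic strength, neither of which the documents give. It also assumes that 40 patients are randomized. The notes to Table 2 refer to open enrollment beside a randomization arm, and with fewer randomized the imbalance would be larger in proportion. I would class this as a change to consider.

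**What to change.** 1. Generate the permuted blocks of 2 and 4 as two lists, by respiratory failure at randomization (yes/no), using the definition already in the Primary Endpoint. Use this one factor only.
2. Make the primary estimate match: take the day-30 Kaplan-Meier failure-free difference within each stratum, combine the two with weights equal to each stratum's share of the randomized patients, and base the one-sided 90% confidence interval on the combined standard error.
3. Use the same binary factor to define the prevention and treatment subgroups.

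The cost is one additional list from the study statistician and a sentence in each of the allocation and confidence-interval paragraphs. The downside is that total arm sizes may differ by up to 4, against 2 with a single list. If enrolment has already begun on one list, step 2 alone recovers most of the precision, provided both arms are represented in each stratum.

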In cohort 1, we will enroll patients to test the safety, tolerability and toxicity in moderate to severe COVID-19 patients. Initial subjects in cohort 1 will receive a loading dose of 5.0 μ g/kg (not to exceed 400 μ g) over 30 minutes followed by a low dose infusion of 1.44 μ g/kg/hr. Toxicity of Regadenoson treatment will be graded by using the Common Terminology Criteria for Adverse Events (CTCAE) Criteria version 4.03 in this trial. If two dose limiting toxicities occur at a loading dose of 5.0 μ g/kg then the loading dose will be halved to 2.5 μ g/kg and enrollment will continue. If two dose limiting toxicities occur at a loading dose of 2.5 μ g/kg then the Data and Safety Monitoring Board (DSMB) will convene to determine if the study should continue and omitting the loading dose may be considered. Alternatively, the DSMB will convene after 5 out of 5 patients or 5 out of 6 patients tolerate a given loading dose to make a determination on moving forward to cohort 2. Otherwise, the trial will be terminated. (please see the details in the Detailed DSMB Plan section)

The sickle cell trial and our phase 1 trial in lung transplant patients did not show any renal/hepatic toxicity. Because COVID-19 itself may cause renal injury, we will closely monitor the renal and hepatic function of these patients per their standard of care. To assess safety of each subject, we will tabulate sequentially the number of participants

who unexpectedly experience serious cardiovascular side effects or persistent (> 30 min) intolerable side effects. If at any point in the accrual, the posterior probability exceeds 90% that the risk of at least one serious side effect for participants in the Regadenoson arm is more than 10 percentage points greater than in the standard care arm, we will stop the trial.

Adverse Event (AE) Recording and Reporting:

All adverse events will be collected starting at time of consent through POD 30. Adverse events will be recorded on a case report form and will be assessed for seriousness, severity, attribution and expectedness by the site Principal Investigator. A serious cardiovascular side effect is defined as a sustained change (> 5 minutes) in systolic blood pressure >30 mm Hg or systolic blood pressure <75 mm Hg, tachycardia >130 bpm, or bradycardia <40 bpm.

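### The safety tabulation counts only participants with unexpected serious side effects; the qualifier is undefined, conflicts with the rest of the rule, and can cost the boundary detection if applied literally

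*Combined protocol and SAP*

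**What the plan says.** Under Sample Size and Statistical Analysis, the DSMB statistician is to "tabulate sequentially the proportion of participants in each group who unexpectedly experience serious cardiovascular side effects or persistent (> 30 min) intolerable side effects". The sentence ends with the phrase "based on clinical experience with Regadenoson", and the next one adds: "Intolerable side effects include headache or dyspnea". The rule follows: "If the lower bound of a one-sided 80% confidence interval for the difference in proportions exceeds 10%, we will pause the trial". Its operating characteristics are given for an event described without the qualifier: "true proportion of patients who experience serious side effects is 20% in each group, there is a 16.5% chance that the trial will be paused". The second figure is 58%, for a Regadenoson rate of 40%.

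The Safety Assessments section repeats the tabulation with the same qualifier: "who unexpectedly experience serious cardiovascular side effects". The stopping sentence that follows it there (a 90% posterior probability of an excess above 10 percentage points) refers to at least one serious side effect, with no mention of expectedness.

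Under Adverse Event (AE) Recording and Reporting, a serious cardiovascular side effect is defined by fixed blood-pressure and heart-rate thresholds, again with no expectedness condition. The same section says that adverse events "will be assessed for seriousness, severity, attribution and expectedness by the site Principal Investigator".

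In the DSMB plan, the adverse event definitions list anticipated events that are not to be recorded, and shortness of breath is among them. Adverse Event Recording then makes an exception for events that meet the serious adverse event criteria.

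**The concern.** A safety boundary needs a numerator that two people would count the same way. This one has a qualifier with no definition of its own. The only expectedness assessment the plan describes is the adverse-event judgement recorded on the case report form, so someone applying the tabulation literally may turn to it. The events being watched are of types the plan already associates with the drug. Safety Assessments refers to its cardiac risk, the dose justification mentions bronchoconstriction and unpleasant effects of rapid injection, and the toxicity grading table lists arrhythmias, headache and bronchospasm. A literal reading can therefore drop known effects from a rule meant to detect an excess of them.

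At stake is whether a real excess on Regadenoson reaches the boundary as often as the plan says. The wording also leaves unclear which event the 16.5% and 58% describe.

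**Working it through.** **Inputs.** From Sample Size and Statistical Analysis: 40 participants, 1:1, permuted blocks of 2 and 4; pause if the one-sided 80% lower bound exceeds 0.10; scenarios 20% v 20% and 40% v 20% (the 20% control rate in the second is carried over from the first). From Scheduling, Timing, and Organization of Meetings: DSMB meetings after 15, 25 and 40 enrolled, *assumed* here to be the looks, since the rule itself says only that the tabulation is sequential. The share of events filtered as expected is *not in the documents* and is varied below.

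**Rule.** With observed proportions p1 (Regadenoson) and p0 (control), pause if p1 − p0 − 0.8416 × √[p1(1 − p1)/n1 + p0(1 − p0)/n0] > 0.10.

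**One worked outcome at 20 per arm.**
- All events counted, 10 v 4: 0.50 − 0.20 − 0.8416 × √(0.0125 + 0.0080) = 0.30 − 0.8416 × 0.1432 = 0.179. This exceeds 0.10, so the trial pauses.
- Half filtered in each arm, 5 v 2: 0.25 − 0.10 − 0.8416 × √(0.009375 + 0.0045) = 0.15 − 0.8416 × 0.1178 = 0.051. No pause.

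**Reproducing the plan's figures** (exact binomial enumeration of the rule).
- Single look at 20 per arm: 4.9% and 43.7%. This does not match the stated 16.5% and 58%.
- Looks at 15, 25 and 40, with the odd participant at each of the first two looks in either arm: 16.1% to 17.2% and 58.4% to 61.7%. The split 8/7, 13/12, 20/20 gives 16.1% and 58.4%.
- Simulated permuted blocks: about 16.5% and 60%.

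The stated figures are thus consistent with a three-look rule in which the counted event has true rates of 20% and 40%.

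**Effect of a filter when the true rates are 20% v 40%** (looks at 15/25/40; the range covers the four splits):

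| Assumption | Rates as counted (control v Regadenoson) | Pause probability |
|---|---|---|
| No filter | 20% v 40% | 58.4–61.7% |
| Half of events removed in both arms | 10% v 20% | 35.3–36.8% |
| Three quarters removed in both arms | 5% v 10% | 15.0–17.0% |
| Half of the drug excess removed | 20% v 30% | 34.8–38.0% |
| All of the drug excess removed | 20% v 20% | 16.1–17.2% |
| 10 points of shared background removed | 10% v 30% | 62.4–64.0% |

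The last row matters: the direction depends on *which* events are removed. If only background common to both arms goes, detection does not fall.

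**False pauses when the arms are truly equal.** A filter also lowers these: from about 16.5% at 20% v 20% to 9.7–11.1% at 10% v 10%. If every qualifying event is counted and the background is 30% per arm, the rate is about 19%.

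**A second route to undercounting.** Dyspnea is named as a counted intolerable side effect. Shortness of breath is on the list of anticipated events that are not recorded, with an exception only if the event is serious. A persistent but non-serious episode would meet the boundary's definition and yet might never be recorded. Deleting *unexpectedly* does not repair this.

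**The case against.** Three stronger readings are tempting, and the documents do not support them.

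*The watched events are known, therefore expected, therefore excluded.* Choosing event types from experience with the drug does not make serious, sustained instances of them expected. The protocol reports no dose-limiting toxicity at the low infusion dose. Its only definition of unexpected, given for unanticipated problems, covers nature, severity or frequency, so a known effect that is worse or more common than foreseen would still qualify. The fixed thresholds and the naming of headache and dyspnea suggest the authors may have meant to count known effects. No section says they are excluded.

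*The rule has lost its stated detection rate.* The wording of the scenario, "if the true proportion of patients who experience serious side effects is 20% in each group", may be shorthand for the counted event. If 20% and 40% are rates of the event as counted, 16.5% and 58% stand. The filtered shares above are illustrations without a source.

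*The investigator decides what enters the boundary.* The plan gives the expectedness assessment to the site Principal Investigator but the boundary tabulation to the DSMB statistician, and nothing links the two. The trial is double-blind, so a filter could not knowingly be applied by arm.

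The consequence is also cushioned. The DSMB reviews adverse event data at each meeting, receives unblinded reports and a listing of all adverse events, and may pause or halt the trial at any time. The cohort 1 toxicity rule has no expectedness condition.

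What remains after all this is an undefined word in the numerator of a safety rule, at odds with three unqualified statements of the same event. The two readings can give materially different protection, and the plan does not choose between them.

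**Conclusion.** The point holds as an ambiguity with a possible cost, and should be corrected. The qualifier appears in both tabulation sentences, is undefined for this rule, and conflicts with the threshold definition, the stopping sentence and the event behind the stated pause probabilities. Applied literally it *can* reduce the chance of pausing at 20% v 40% from about 60% to about 36% (half of events filtered in both arms) or about 16% (three quarters). These figures rest on assumed looks at 15, 25 and 40, the simple Wald interval, and filtered shares that the documents do not give. They are not estimates of what will happen in this trial.

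**What to change.** Delete *unexpectedly* from the tabulation sentence under Safety Assessments and from the one under Sample Size and Statistical Analysis. State that every participant who meets the existing serious cardiovascular definition, or has a persistent intolerable side effect as already described, is counted in each arm regardless of expectedness or attribution. Say that the 16.5% and 58% refer to that event, and name the looks behind them.

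Reconcile this with the anticipated-event list and Adverse Event Recording in the DSMB plan, so that shortness of breath meeting the persistent intolerable definition is recorded and counted although it is on the list of events not recorded.

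The margin, the confidence level and the pause action stay as they are. The cost is a few words, plus recording some events that would otherwise be left out. Because more events are counted, the false-pause rate is higher than under a filtered count: about 16.5% at a true 20% rate per arm, as the plan already states, and about 19% if the background rate is 30%. The DSMB should be told this when it reviews the monitoring plan.

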A Detailed Justification for The Proposed Dose, Dosing range, Number of Doses, and Dose Interval: Regadenoson will be given intravenously as 5 µg/kg loading dose over 30 mins (to avoid unpleasant side effects sometimes associated with the rapid bolus injection of Regadenoson), followed by a continuous slow infusion (1.44micrograms/kg/hour) with the use of a pediatric infusion pump for 6 hours. The initial high dose (5 µg/kg) infusion is based on: Regadenoson is a FDA approved drug for myocardial perfusion imaging with a bolus dosing (400 micrograms, in 10 seconds). The initial dose (5 μg/kg) is lower than the MPI dose (400 µg). And it will be given slower as a bolus over 30 mins. The low dosage (1.44micrograms/kg/hour) slow infusion is based on the Sickle cell disease phase II clinical trial and our clinical phase I trial in lung transplant patients. Both trials have demonstrated that low dosage infusion(1.44micrograms/kg/hour) is safe with no dose limiting toxicities up to 12 hours (above reference #30). A loading dose is needed in the present study to get effective drug concentrations to the patients as soon as possible after diagnosis of cytokine storm syndrome. We will keep Aminophylline, a competitive adenosine receptor antagonist, on hand as a rescue medication for rare side effects of Regadenoson, such as bronchoconstriction. Aminophylline has been used to terminate persistent pharmacodynamic effects. In such case, aminophylline may be administered in doses ranging from 50 mg to 250 mg by slow intravenous injection (50 mg to 100 mg over 30-60 seconds).

Trial Timeline

Timeline: Please see the attached for the detailed (Table 2) projected timeline for each patient. A loading dose is needed in the present study to get effective drug concentrations to the patients as soon as possible after diagnosis of cytokine storm syndrome in hospitalized COVID-19 patients. We propose to treat a total of 40 moderate to severe COVID-19 patients in this protocol. In this trial, the discontinuation from study drug is defined as any subject discontinuing Regadenoson treatment or discontinuing from the study post drug treatment for any reasons (such as, COVID-19

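### A reaction that needs the rescue antagonist, or that stops the infusion, is scored as no boundary event if it resolves within 30 minutes without a qualifying cardiovascular change

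*Combined protocol and SAP*

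**What the plan says.** **The counted event.** Under Sample Size and Statistical Analysis, the DSMB statistician tabulates by arm the participants "who unexpectedly experience serious cardiovascular side effects or persistent (> 30 min) intolerable side effects, based on clinical experience with Regadenoson". The same section adds: "Intolerable side effects include headache or dyspnea". The Safety Assessments section describes the same tabulated event next to a second rule, which stops the trial on a posterior probability above 90% that the excess risk exceeds 10 percentage points.

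**The cardiovascular limb.** The synopsis section Adverse Event (AE) Recording and Reporting says: "A serious cardiovascular side effect is defined as a sustained change (> 5 minutes) in systolic blood pressure >30 mm Hg". It then lists systolic pressure below 75 mm Hg, heart rate above 130 and heart rate below 40, without making clear whether the 5 minutes govern these as well.

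**The pause rule.** "If the lower bound of a one-sided 80% confidence interval for the difference in proportions exceeds 10%, we will pause the trial". The stated chance of a pause is 16.5% when both true rates are 20%, and 58% when the regadenoson rate is 40%.

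**The antagonist.** The dose justification in Volume 2 says: "We will keep Aminophylline, a competitive adenosine receptor antagonist, on hand as a rescue medication for rare side effects of Regadenoson, such as bronchoconstriction". It continues: "Aminophylline has been used to terminate persistent pharmacodynamic effects". It does not say how long after onset the antagonist is given.

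No section says that use of the antagonist, or interruption of the infusion for a reaction, counts towards the boundary.

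**The concern.** A duration threshold is a reasonable way to keep trivial symptoms out of a safety count. It works poorly when treatment can shorten the symptom, because duration then measures how quickly someone intervened as well as how bad the reaction was. Bronchoconstriction that is treated and gone in 10 minutes does not count. Milder dyspnea left alone for 31 minutes does.

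The loss would not be balanced. The antagonist competes with the study drug at its receptor, so it shortens drug effects in particular, and the missing events would come mainly from the regadenoson arm. That lowers the between-arm difference on which the pause rule acts. The pause is also what triggers the planned look at adverse event profiles and dosing, so an undercount can delay that review.

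**Working it through.** **1. Inputs.** From Sample Size and Statistical Analysis: "The total sample size of 40 participants will be randomized equally between the usual care and Regadenoson groups", so 20 per arm; one-sided 80% interval, z = 0.8416; margin 0.10; true rates 20%/20% and 40%/20%. From the Volume 3 section on scheduling of meetings: DSMB meetings after 15, 25 and 40 participants. The plan does not say which looks or interval formula its figures use, so these meetings and the Wald formula are assumptions, tested in step 2.

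**2. The plan's own figures.** The rule is: pause if L > 0.10 at any look, where

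L = p_R − p_C − 0.8416 × √[p_R(1 − p_R)/n_R + p_C(1 − p_C)/n_C].

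Exact binomial enumeration gives:

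| Looks (regadenoson/control) | 20% vs 20% | 40% vs 20% |
|---|---|---|
| Plan, as stated | 16.5% | 58% |
| 8/7, 13/12, 20/20 | 16.1% | 58.4% |
| 7/8, 12/13, 20/20 | 17.2% | 61.7% |
| 20/20 only | 4.9% | 43.7% |

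The three-look rule reproduces the stated figures. In this calculation the rate entered is the counted rate, so the figures describe the true rate only if every true event is counted.

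**3. What one uncounted patient does.** Take the final look with 4/20 events in control.

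- 9/20 on regadenoson: difference 0.25, SE = √(0.45×0.55/20 + 0.20×0.80/20) = 0.1427, L = 0.25 − 0.120 = 0.130. Pause.
- 8/20 on regadenoson: difference 0.20, SE = √(0.40×0.60/20 + 0.20×0.80/20) = 0.1414, L = 0.20 − 0.119 = 0.081. No pause.

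A single reclassified participant can decide the outcome.

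**4. Effect on the pause probability.** Let f be the share of the regadenoson-arm excess that is shortened below the threshold. The documents give no value for f. With true rates of 40% and 20%, the counted regadenoson rate is 0.40 − 0.20f. Using looks 8/7, 13/12, 20/20:

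| f (assumed) | Counted rate | Lost events, % of treated patients | Chance of a pause |
|---|---|---|---|
| 0 | 40% | 0 | 58.4% |
| 5% | 39% | 1% | 56.0% |
| 10% | 38% | 2% | 53.6% |
| 25% | 35% | 5% | 46.4% |

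The last row corresponds to one treated patient in 20. With the odd participant placed in control, the three losses take the pause probability from about 62% to 59%, 57% and 50%, so the falls are similar.

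**5. Which limbs are affected.** For dyspnea and headache the 30-minute threshold is explicit. In the cardiovascular limb, only the systolic change above 30 mm Hg is clearly tied to a duration. If the other three criteria carry none, a brief excursion meeting one of them counts despite treatment.

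**The case against.** Four points can be made on the other side.

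- **Timing is not stated.** The plan speaks of ending persistent effects, the same word that the boundary uses for more than 30 minutes, so the antagonist might be given after the threshold has passed. Stopping the infusion also need not end symptoms quickly: Volume 2 gives an intermediate half-life averaging 30 minutes and a terminal one of about 2 hours after injection. This stands, and it is why the size is unknown. It does not remove the gap, because nothing prevents earlier use.
- **The rescued effects are called rare.** A reader might infer that half or three quarters of the excess could vanish. Three quarters of a 20-point excess is 15% of treated patients, which does not fit that description. Losses of that order are not supported.
- **Other safeguards exist.** A rescued reaction that is a serious adverse event must be recorded and, if possibly related, reaches the DSMB within 7 days. Cohort 1 has a dose-limiting toxicity rule, Table 1 grades bronchospasm without a duration, and the DSMB may halt at any time. These limit the consequence, but none alters the boundary count. Shortness of breath and wheezing are on the Volume 3 list of anticipated events that go unrecorded unless serious, and no grade is given that makes a toxicity dose-limiting.
- **The cardiovascular limb is less exposed.** A reader might infer that every counted event must outlast a set time, or that pressure support in a ventilated patient would hide a fall below 75 mm Hg. The text is ambiguous on whether the 5 minutes apply there, so neither inference is secure.

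**Conclusion.** The gap is real but narrow. As written, a reaction that led to rescue or to stopping the infusion, and that resolved within 30 minutes without a qualifying cardiovascular change, is scored as no event. It is clearest for dyspnea and bronchoconstriction. In the cardiovascular limb it applies for certain only to the systolic change above 30 mm Hg.

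A reader might infer that the stated 16.5% and 58% are wrong. They are not: they reproduce, and the event definition only affects which rate they describe. Under assumed losses of 5% to 25% of the excess, the chance of a pause at true rates of 40% versus 20% is about 56% to 46% instead of 58%, with the smaller losses more likely given the plan's own wording. This rests on three looks, the Wald interval, and loss confined to the regadenoson arm. It is a cheap improvement to a rule that the plan puts first, since safety analysis is prioritized; the existing calculation needs no correction.

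**What to change.** In Safety Assessments and in Sample Size and Statistical Analysis, add that a participant also counts as having a boundary event, in either blinded arm and whatever the duration, if the rescue antagonist was given for a suspected study-drug effect, or if the study infusion was interrupted or stopped for one. State in the same place whether the 5-minute requirement governs all four cardiovascular criteria or only the first.

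Add both items to the case report form. Table 2 asks only for available medications to be recorded, so capture of rescue use and infusion interruption should not be taken for granted. Then re-run the two pause probabilities at the event rates expected under the widened definition. A separate criterion for vasopressor use is not needed.

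The cost is a sentence in two places, two form fields and a short recalculation. The downside is a few more counted events, some of them resting on a clinician's judgement that the study drug was to blame; masking and the same definition in both arms limit that. The change concerns only what is counted. When rescue is given or the infusion is stopped is left as it is.
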